7.1 Sample Size Justification

Sample Size Calculation

The proposed study is a single-arm registry which will run concurrently with the INVEST feasibility study. A sample size of 200 provides 180 subjects at 180 days, with an estimated 10% attrition rate. Since this is a single- arm study of Apollo / Artemis MIES treatment, a formal hypothesis test is not planned. Assuming an effectiveness primary endpoint response rate for mRS 0 to 3 of 34% (61/180), the expected normal approximation to the binomial two-sided 95% confidence interval around the primary endpoint rate is (27%, 41%). Hence, the proposed sample size provides a precision estimate of \pm 7% which is sufficient to assess the Apollo / Artemis MIES treatment. The precision for the estimated single proportion was calculated using SAS v 9.4 (SAS Institute, Cary, NC).

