INVEST-REGISTRY: Minimally Invasive Endoscopic Surgical Treatment With Apollo/Artemis in Patients With Brain Hemorrhage: A Prospective Multicenter Registry [name] NCT02661672 Document Date: 10-24-2017

INVEST-REGISTRY: Minimally Invasive Endoscopic Surgical Treatment with Apollo / Artemis in patients with Brain Hemorrhage: A Prospective Multicenter Registry

[name] Mount Sinai School of Medicine

[name] Stony Brook Medical Center

[name] Semmes-Murphy Clinic

Version 1.0	11-5-2015
Version 2.0	03-30-2017
Version 3.0	10-24-2017

Study Title: INVEST REGISTRY: Minimally Invasive Endoscopic Surgical Treatment with Apollo / Artemis in patients with Brain Hemorrhage: A Prospective Multicenter Registry

Version Number: 3

Version Date: 10-24-2017

Study Center:

I, the undersigned, have read and understand the protocol specified above and agree on its content. I agree to perform and conduct the study as described in the protocol and in accordance with the relevant parts of the appropriate regulatory requirements and the pertinent individual country laws/regulations.

Investigator	
Print name:	

Date

Primary Contacts

Penumbra Inc.
[name]
Statistical and Data Management Center
Mount Sinai School of Medicine
[name]
Statistical and Data Management Center Mount Sinai School of Medicine [name]
[name]
Oculus Imaging LLC
[name]
[name]
-

Study Synopsis:

Title: INVEST REGISTRY: Minimally Invasive Endoscopic Surgical Treatment with Apollo / Artemis in patients with Brain Hemorrhage: A Prospective Multicenter Registry

Objective: The primary objective of this multicenter prospective registry is to provide additional safety, technical outcomes and clinical outcomes data for minimally invasive endoscopic surgery (MIES) with Apollo / Artemis for the evacuation of supratentorial brain hemorrhage in adult patients who do not qualify for the concurrent INVEST Feasibility study at active United States (US) INVEST centers.

Study Design: This study will be a prospective, non-randomized, multi-center, single arm registry that will enroll up to 50 patients at up to 30 US centers.

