4.4 Study Visits

Subjects enrolled to this study will follow the below visits schedule according to standard of care for stroke patient follow-up.

- Pre-Treatment
- Procedure
- Post procedure (24 hours, Apollo / Artemis MIES patients)
- 7 days post-enrollment or Discharge (whichever comes first)
- 1 month follow-up (+/- 14 days)
- 3 month follow-up (+/- 21 days)
- 6 month follow-up (+/- 28 days)

4.5 *Recruitment*

The target population for the INVEST registry are adult patients who have a diagnosis of supratentorial intracranial hemorrhage who do not require emergent open surgical decompression related to uncontrolled intracranial pressure or mass effect, who do not qualify for the INVEST multi-center Feasibility and who are to be treated with Apollo or Artemis MIES at an INVEST center.

Potential study participants and/or their legal authorized representative will be identified by the study team at each site to obtain consent and determine eligibility. Up to 30 United States sites will be included in this study and enroll up to 50 patients.

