6.1.1 Definition of Analysis Samples

1. Target Population

The target population for the INVEST registry are adult patients who have a diagnosis of supratentorial intracranial hemorrhage who do not require emergent open surgical decompression related to uncontrolled intracranial pressure or mass effect, who do not qualify for the INVEST multi-center Feasibility study and who are to be treated with Apollo / Artemis MIES at an INVEST center.

2. Intent to Treat Sample

As the primary analysis, all efficacy and safety outcome measures will be analyzed under the intent-to-treat (ITT) principle. Under this principle, the evaluable sample includes all subjects who are enrolled.

3. Per Protocol Sample

In addition to the defined ITT analysis sample, a per-protocol sample is defined as a subset of the ITT sample. This sample will be used for secondary sensitivity analyses of the primary and secondary outcomes.

The per-protocol sample will include all subjects that do not have the following protocol violations or deviations:

- a. Eligibility violation
- b. Treatment failure (no Apollo / Artemis MIES performed)
- c. Missing 180-day primary efficacy outcome (not including missing due to death prior to the 180 days)
- 4. As Treated Sample

This sample will be used for analyses of the safety outcomes. The as treated sample will include all subjects that are enrolled and have Apollo / Artemis MIES performed.

7. General Statistical Considerations

General Design Issues

The primary objective of this multicenter prospective registry is to provide additional safety, technical outcomes and

clinical outcomes data for minimally invasive endoscopic surgery (MIES) with Apollo / Artemis for the evacuation of brain hemorrhage in patients who do not qualify for the concurrent INVEST feasibility study at active INVEST centers. This structure will allow INVEST centers to consider all patients presenting with intracranial hemorrhage who are potentially candidates for the Apollo / Artemis MIES procedure for a clinical research trial, which will facilitate enrollment as well as protocol familiarity and adherence. This structure will also yield the highest possible amount of data about this new procedure.

General Statistical Methods

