7.3 Missing Data and Imputation Methods

Under the ITT principle, all patients who are enrolled are included in the analysis. Therefore, missing data, especially in the outcome measures, can be problematic. Every effort is to be made to keep all missing data, particularly the Day 180 outcomes, to a minimum. Despite the clinical sites' best efforts, some missing data may be inevitable mainly due to lost-to-follow-up (LTFU). The number and proportion of subjects eligible for and compliant with each follow-up examination will be presented. Subjects who withdraw from the study will be tabulated with reasons for withdrawal. Since the primary endpoint is defined using mRS, subjects deceased during study follow-up will be scored as mRS 6. Other subjects not completing the 180-day follow-up visit will be categorized for the primary endpoint using the mRS as of the last available follow-up visit or discharge (whichever is later). As a sensitivity analysis, we will also perform analysis after excluding subjects without 180-day follow-up evaluations. Additional details will be provided in the Statistical Analysis Plan (SAP).

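### Section 7.1 justifies ±7-point precision with 200 enrolled and 180 followed, but the synopsis and section 4.5 cap enrolment at 50, where the same method gives ±13 to ±14 points

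*Combined protocol and SAP*

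**What the plan says.** The Sample Size Justification (section 7.1) states: "A sample size of 200 provides 180 subjects at 180 days, with an estimated 10% attrition rate". It assumes that 34% of patients (61/180) reach an mRS of 0 to 3 and gives a two-sided 95% interval, by normal approximation, of 27% to 41%. It summarises this as a precision of ±7%, "which is sufficient to assess the Apollo / Artemis MIES treatment". The same section says that no formal hypothesis test is planned.

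Two other places give a different size. The Study Design paragraph of the synopsis describes a "single arm registry that will enroll up to 50 patients at up to 30 US centers". Section 4.5 (Recruitment) says: "Up to 30 United States sites will be included in this study and enroll up to 50 patients".

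Two further sections fix the denominators. For the intent-to-treat sample, section 6.1.1 says: "Under this principle, the evaluable sample includes all subjects who are enrolled". Section 7.3 scores deaths as mRS 6. It says that other patients without a 180-day visit "will be categorized for the primary endpoint using the mRS as of the last available follow-up visit or discharge". As a sensitivity analysis, "we will also perform analysis after excluding subjects without 180-day follow-up evaluations".

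**The concern.** A registry that stops at 50 cannot enrol 200 or follow 180, so the precision in section 7.1 does not describe the study set out in the synopsis and section 4.5.

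This matters for two reasons. First, with no hypothesis test planned, precision is the only reason given for the size of the registry. If 50 is the true limit, the protocol has no valid sample-size justification, and a reader of 7.1 alone, such as an ethics committee or DSMB member, would expect an interval about half as wide as the one obtainable. The rationale section says the data may inform a later pivotal trial, so the expected precision matters to later users too. Second, the permitted enrolment is itself unclear, by a factor of four (200/50).

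**Working it through.** **Inputs.** From section 7.1: 200 enrolled, attrition 10%, rate 34% (61/180), two-sided 95% normal-approximation interval. From the synopsis and section 4.5: at most 50 enrolled. From sections 6.1.1 and 7.3: the primary analysis includes everyone enrolled, with missing 180-day mRS filled in.

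**Formula.** Half-width = 1.96 × √(p(1 − p)/n).

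**Step 1: reproduce the plan's figure.**
- 200 × 0.90 = 180.
- p = 61/180 = 0.339. Half-width = 1.96 × √(0.339 × 0.661/180) = 0.069.
- Interval: 27.0% to 40.8%, which rounds to the stated 27% to 41% and ±7 points.

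Section 7.1 is therefore arithmetically correct for its own n.

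**Step 2: find the denominators under the cap.**
- Primary analysis: all enrolled, so at most 50.
- After the plan's attrition: 50 × 0.90 = 45. This parallels the step from 200 to 180 in section 7.1. It also approximates the sensitivity analysis in section 7.3, on the assumption that the 10% describes the patients who lack a 180-day evaluation.

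**Step 3: apply the same method at p = 0.34**, so that p(1 − p) = 0.2244.

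| n | Basis | Half-width | 95% interval |
|---|---|---|---|
| 50 | All enrolled, at the cap | 1.96 × √(0.2244/50) = 13.1 points | 20.9% to 47.1% |
| 45 | Cap less 10% attrition | 1.96 × √(0.2244/45) = 13.8 points | 20.2% to 47.8% |
| 180 | Section 7.1 | 1.96 × √(0.2244/180) = 6.9 points | 27.1% to 40.9% |
| 200 | All enrolled, if 200 is intended | 1.96 × √(0.2244/200) = 6.6 points | 27.4% to 40.6% |

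Relative to n = 180, the half-width grows by √(180/50) = 1.90 and √(180/45) = 2.00.

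**Step 4: how far the cap is from ±7 points.** n = 1.96² × 0.2244/0.07² = 175.9, so 176 analysed patients, about 3.5 times the cap.

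**Step 5: does the interval method matter?** Exact (Clopper-Pearson) intervals are 21.2% to 48.8% for 17/50 and 20.0% to 49.0% for 15/45. The conclusion does not depend on the normal approximation.

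**Step 6: can the two sizes be read together?** A per-site reading of 50 gives 30 × 50 = 1,500, not 200, and the synopsis wording describes the whole registry. Because 50 is a maximum, 200 cannot be an upper scenario. Section 7.1 speaks of this registry's proposed size, not of a pool with the feasibility study.

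**The case against.** The best reply is that little follows in practice. The cohort results are descriptive, and section 7.2 reports the primary endpoint as a proportion with a 95% interval based on the patients actually analysed. A reader of the results will see the true width whatever section 7.1 says. This stands: the estimate is not biased and the planned primary analysis need not change. It does not repair a planning justification that relies on an n ruled out elsewhere, nor does it settle how many patients may be enrolled.

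A second point concerns the 45. Section 7.3 does not say whether patients who died are kept when those without a 180-day evaluation are excluded, and section 7.1 does not say whether its 10% includes deaths. If deaths were excluded, the sensitivity analysis could have fewer than 45 patients and a different response rate. This also stands, so 45 is best described as the cap less the plan's attrition. The figure for 50 does not depend on it.

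Third, section 7 (General Statistical Methods) also provides for tests between subgroups at the 0.05 level, so the analysis is not wholly free of testing. Section 7.1 does not size the registry for those tests, and the contradiction is unaffected.

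Finally, the cap appears twice and 200 once, but a synopsis and a body section may simply repeat each other. The count suggests that 50 is the intended number; it does not prove it.

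**Conclusion.** The contradiction is real and the protocol is wrong as written. At the cap of 50, the plan's own method and 34% rate give ±13.1 points for all enrolled and ±13.8 points for 45, against the stated ±7. These are best cases under the cap, since fewer than 50 patients would widen them. If 200 is the intended size, the precision claim holds (±6.9 points for 180, ±6.6 for 200), and the error lies in the synopsis and section 4.5 instead. The result rests on the plan's assumed rate and, for the n of 45 only, on its assumed 10% attrition.

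**What to change.** Decide which enrolment number is intended and make the synopsis, section 4.5 and section 7.1 agree.

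- **If 50 stands:** replace the 200 and 180 figures, the 27% to 41% interval and the ±7% sentence in section 7.1. Suggested content: up to 50 patients; at a 34% rate the expected two-sided 95% interval (normal approximation) is about 21% to 47% (±13 points) for all 50 enrolled, or about 20% to 48% (±14 points) for 45 after 10% attrition. Then say whether that precision is enough for the registry's purpose, and why, or withdraw the adequacy claim.
- **If 200 is intended:** correct the limit in the synopsis and section 4.5, and leave the precision in section 7.1 as it is.

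The first option costs one paragraph and a less favourable stated precision. The second changes one number in each of two places, but it raises the stated enrolment limit fourfold, which is more than an editorial correction. Neither changes the data collected per patient or the analysis methods, and this point does not ask for more patients.

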7.4 Secondary Statistical Analysis

7.4.1 Secondary Endpoints

The secondary effectiveness variables:

- mRS at 30 and 90 days The number and percentage of subjects who experience mRS 0 to 3 will be calculated along with the 95% confidence interval. Frequency counts and percentage of subjects within each category will be provided.
- Length of hospital stay The median total length of stay and median ICU length of stay along with the interquartile range will be provided.
- Requirement for VPS The number and percentage of subjects who have VPS placement will be calculated along with the 95% confidence interval.

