7.5 Safety Analysis

7.5.1 Safety Outcomes

Several specific adverse events are monitored throughout the study. However the primary safety outcome to be assessed at completion of the trial will be death within 30 days.

The proportion of deaths for any reason through 30 days will be calculated and a 95% confidence interval will be presented. Survival estimates will be generated to evaluate the time-to-death using the Kaplan-Meier methodology for all deaths through 30 days.

All adverse events will be summarized by showing the number and percent of patients which report the event. Events will also be reported by relationship to the procedure or device.

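### The stated ±7-point precision is not attainable at the 50-patient cap, and no interval method is named for the reported proportions

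*Combined protocol and SAP*

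**What the plan says.** Section 7.1 (Sample Size Justification) starts from this statement: "A sample size of 200 provides 180 subjects at 180 days, with an estimated 10% attrition rate". It assumes that 34% of patients (61 of 180) reach mRS 0 to 3. From that it derives a "normal approximation to the binomial two-sided 95% confidence interval" of 27% to 41%, and describes the resulting ±7% as a precision "which is sufficient to assess the Apollo / Artemis MIES treatment".

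The Synopsis says the registry "will enroll up to 50 patients at up to 30 US centers", and Section 4.5 repeats both limits.

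For the analysis itself:

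- Section 7.2 promises a 95% interval for mRS 0 to 3 at 180 days and another for surgical success.
- Section 7.4.1 promises one for mRS 0 to 3 at 30 and 90 days, and for shunts: "The number and percentage of subjects who have VPS placement will be calculated along with the 95% confidence interval".
- Section 7.5.1 does so for 30-day mortality: "The proportion of deaths for any reason through 30 days will be calculated and a 95% confidence interval will be presented". Adverse events get counts and percentages only.

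None of these sections names a method. The General Statistical Methods text under Section 7 says only that intervals are two-sided, and leaves analysis detail to a statistical analysis plan to be finalised before database lock.

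**The concern.** There are two linked problems. First, the precision statement describes a registry of 180 evaluable patients, whereas the design allows at most 50 enrolled. A reader who relies on Section 7.1 would expect intervals about half as wide as the registry can give.

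Second, the only interval formula for a proportion in the documents is the one used for that planning calculation. It behaves well at 180 patients and a rate near one third. It behaves less well at 50, and poorly when the observed proportion is close to 0 or 1. A programmer with no other instruction could reasonably carry it over.

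Sections 2 and 7.1 both say that no formal hypothesis test is planned, so the intervals carry most of the statement of uncertainty. The rationale for the design says the data may inform a later pivotal trial, so over-optimistic precision could be passed forward.

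**Working it through.** **Inputs.** Section 7.1: 200 enrolled, 10% attrition, 180 evaluable, 61/180. Synopsis and Section 4.5: cap of 50. The nearest whole count to 34% of 50 is 17. With the plan's own 10% attrition, 50 × 0.9 = 45, and the nearest count is 15 (33%).

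**Step 1: reproduce the plan's figure.** Normal approximation (Wald): p ± 1.96 × √(p(1 − p)/n). With p = 61/180 = 0.3389 and n = 180, the half-width is 1.96 × √(0.3389 × 0.6611/180) = 0.0691, so the interval is 27.0% to 40.8%. This rounds to the stated 27% to 41%, ±7 points. Wilson (27.4% to 41.1%) and Clopper-Pearson (27.0% to 41.3%) round to the same limits. The attrition step also checks: 200 × 0.9 = 180.

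**Step 2: the same calculation at the cap.** At 34% and n = 50, 1.96 × √(0.34 × 0.66/50) = 0.131.

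| Result | Wald | Wilson | Clopper-Pearson |
|---|---|---|---|
| 17/50 | 20.9% to 47.1% | 22.4% to 47.8% | 21.2% to 48.8% |
| half-width | 13.1 points | 12.7 points | 13.8 points |
| 15/45 | 19.6% to 47.1% | 21.4% to 47.9% | 20.0% to 49.0% |

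The loss of precision comes from the sample size. The choice of method moves the half-width by about one point at most.

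**Step 3: coverage if the normal approximation were used for reporting.** Exact coverage at a true rate p is the sum of the Binomial(n, p) probabilities over all counts x whose interval contains p. It oscillates with p, so averages over a range are more informative than single points. At n = 50:

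| True rates | Wald mean (minimum) | Wilson mean | Clopper-Pearson mean |
|---|---|---|---|
| 27% to 41% | 93.9% (92.0%) | 95.1% | 96.5% |
| 5% to 20% (assumed) | 91.3% (79.9%) | 95.3% | 97.2% |

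By symmetry, the second row also applies to rates of 80% to 95%. For comparison, Wald coverage at the planned n = 180 and 34% is 95.0%.

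**Step 4: extreme counts at n = 50.** At 0/50 the Wald standard error is zero, so the interval is 0% to 0%; Wilson and Clopper-Pearson both give 0% to 7.1%. At 50/50 Wald gives 100% to 100%, while the other two give 92.9% to 100%. At 1/50 the Wald limits are −1.9% and 5.9%, against 0.4% to 10.5% for Wilson.

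**The case against.** The strongest reply is that the plan never commits to the normal approximation for reporting. Section 7.1 uses it for an expected planning interval, and the analysis detail is deferred. This stands. A reader might infer that the registry's published intervals will under-cover, but the documents do not support that. What they show is an unspecified method with one unsuitable cue. Deferral does not remove the point: the analysis plan may be finalised at any time before database lock in an unblinded single-arm study, and naming the method now is easy.

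Three other stronger readings also fail.

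- **That the normal interval is too narrow for the primary endpoint.** At 17/50 it is 26.3 points wide and Wilson is 25.4, so Wilson is slightly narrower and mainly shifts the centre. Coverage at exactly 34% and n = 50 is 92.5%, but it is 94.9% at 33% and 94.5% at 35%. At n = 45 and 34%, Wald and Wilson both cover 94.2%. The average shortfall near the planning rate is about one point.
- **That rare safety events are misreported.** Individual adverse events get no interval. The only safety endpoint with one is 30-day death. The documents give no mortality rate for it, and the rationale describes many of the patients with very low presenting GCS as having injuries from which they cannot recover. Nothing suggests a count near zero.
- **That intervals within ICH and IVH subsets fail badly.** Section 7.2 promises one interval for surgical success overall, and neither subset sizes nor subset intervals are specified.

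It is also fair to say that the conflict between 200 and 50 is the larger problem in Section 7.1. Settling it would not by itself name an interval method.

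**Conclusion.** The point holds in two parts of unequal weight. The firm part is that the ±7-point precision cannot be delivered under the enrolment cap. At 50 patients and 34% the half-width is about 13 points, nearly double, by any of the three methods.

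The conditional part is that the method for the reported intervals is not stated. Only if the planning formula is carried over does coverage fall, to about 94% on average near the planning rate and about 91% over rates of 5% to 20% or 80% to 95%. Those more extreme rates are assumptions, because the documents give no expected rate for shunt placement or surgical success. These are the two endpoints where the choice could show, and only if their rates turn out to be extreme.

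The denominators of 50 and 45 are also assumptions: enrolment reaching the cap, without and with the plan's 10% attrition. Section 7.3 carries the last available mRS forward for patients without a 180-day visit, so the main analysis would sit nearer 50. The sensitivity analysis that excludes those patients would sit nearer 45.

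**What to change.** In Sections 7.2, 7.4.1 and 7.5.1, or once in the general methods text, state that all 95% intervals for a single proportion are Wilson. Clopper-Pearson is a sound alternative if guaranteed coverage is preferred to shorter intervals.

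In Section 7.1, reconcile 200 with the cap of 50 and restate the precision by the named method. For 17/50 it is 22% to 48% (Wilson) or 21% to 49% (Clopper-Pearson). For 15/45, after 10% attrition, it is 21% to 48% (Wilson). The claim that the precision is sufficient should then be argued again for a half-width of about 13 points, or dropped.

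The cost is a few lines of text and one software option, with no change to conduct or data collection. Some intervals will shift or widen slightly, and the stated precision will look less favourable. If the sponsor instead keeps 180 evaluable patients, the printed 27% to 41% is unchanged after rounding under either method.
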